1.0 Study Summary

Study Title	Brain and Meditation (BAM) Study			
Brief Summary	This study is a randomized controlled trial to test the impact of an			
•	app-based meditation program on perceived stress and behavioral and			
	brain correlates of stress. Healthy adult participants between the ages			
	of 25-65 will be enrolled in the study for about 4-5 months.			
Number of study sites	1			
Study Design	Participants will be randomized into one of two groups: the			
	intervention group or the waitlist control group. The intervention			
	group will use a mobile health app for four weeks. Participants will			
	complete pre-intervention, weekly, post-intervention, and 3-month			
	follow-up surveys and tasks.			
Primary Objective	Test for hypothesized group differences in perceived stress and			
	hippocampal-dependent behavior following participation in a 4-week			
	meditation program.			
Secondary	Within the meditation group, determine whether reductions in			
Objective(s)	perceived stress are associated with changes in hippocampal-			
	dependent behavior.			
Research	Healthy Minds Program (HMP) – a mobile health meditation training			
Intervention(s)/	program			
Investigational				
Agent(s)				
Drugs/devices used	Healthy Minds Program (HMP) – a mobile health meditation training			
on study (including	program			
any IND/IDE #)				
Study Population	25-65 year old healthy adults with no significant experience with			
	meditation			
Sample Size	150 participants			
Study Duration for	4-5 months			
individual				
participants				
Study Specific	mHealth = mobile health			
Abbreviations/	HMP = Healthy Minds Program			
Definitions				

2.0 Background

2.1 Relevant prior experience and gaps in current knowledge

Meditation training is known to reduce subjective appraisals of stressful life events, or "perceived stress", but access to in-person programs is limited due to high costs and lack of available services. The hippocampus is a brain region highly sensitive to stressful and adverse life events, and may play a mechanistic role in determining individual differences in perceived stress, a hypothesis that is best tested using an intervention with stress-reducing effects. This project will address each of these current knowledge gaps by studying the impact of a 4-week mobile health (mHealth) meditation training program on perceived stress and hippocampal-dependent behavior.

2.2 Relevant preliminary data

We have conducted similar mHealth studies with educators in Wisconsin (IRB Protocol: 2020-0533) and undergraduate students at UW-Madison (IRB Protocol: 2020-1454). Both studies provided evidence that a large number of participants are willing to download and regularly use the Healthy Minds Program (HMP) app as well as stay engaged in a longitudinal study. We have also identified correlations between elevated perceived stress and compromised hippocampal-dependent behavior in cross-sectional data.

2.3 Scientific background for, rationale for, and significance of the research

Meditation training dramatically reduces perceived stress and has benefits for psychiatric conditions associated with elevated perceptions of stress, such as depression and post-traumatic stress disorder (PTSD). Access to in-person programs, however, is limited due to associated cost and lack of available services.

Research on behavioral and neurobiological mechanisms contributing to individual differences in perceived stress is largely limited to correlational, cross-sectional studies. The inclusion of behavioral outcomes in research on a meditation training program will allow us to draw causal inferences regarding mechanisms of perceived stress.

Prior research has demonstrated that greater roaming entropy, or more diverse activity around one's lived environment, is associated with greater psychological well-being in humans (Heller et al., 2020) and with greater neurogenesis in the hippocampus of laboratory mice. We are interested in examining whether a meditation intervention that seeks to improve well-being will do so in part through effects on greater roaming entropy, and whether individual differences in roaming entropy (either at baseline, or in response to the meditation intervention) are associated with behavioral changes consistent with greater hippocampal neurogenesis.

In this project, we will conduct a randomized controlled trial of the HMP vs. waitlist control to test the efficacy of a fully remote, 4-week meditation intervention on reducing perceived stress in a healthy adult population. Using behavioral measures with a known neurobiological basis (pattern separation and real-world exploratory behavior), we will investigate hypothesized mechanisms associated with individual differences in perceived stress and how they may be impacted by meditation training.

3.0 Study Objectives and Endpoints

3.1 Specific aims

- To assess efficacy of a 4-week mHealth meditation training program on reducing perceived stress.
- To investigate the effects of meditation training on candidate behavioral and brain mechanisms of perceived stress: behavioral pattern separation and real-world experiential diversity.
- To assess the extent to which lower levels of perceived stress following mindfulness training is associated with corresponding changes to these candidate mechanisms.

3.2 Hypotheses

- Intervention participants will show larger reductions in perceived stress relative to waitlist control participants at post-intervention and follow-up timepoints.
- Intervention participants will show improved pattern separation behavior relative to waitlist control participants at post-intervention and follow-up timepoints.
- Intervention participants will show increased real-world "experiential diversity" assessed using GPS location tracking relative to waitlist control participants at post-intervention and follow-up timepoints.
- Changes in hippocampal-dependent behavior will be correlated with reductions in perceived stress.

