3.3 Primary and secondary study endpoints

Primary endpoints

• Scores on the perceived stress scale at post-intervention (T5) controlling for baseline (T1)

Secondary endpoints

- Performance on the behavioral pattern separation task (post-intervention and follow-up/T6)
- PROMIS depression and anxiety (post-intervention and follow-up)

Tertiary and exploratory endpoints

- Symptoms of PTSD measured using the PCL-5 (post-intervention and follow-up)
- PROMIS sleep disturbances (post-intervention and follow-up)
- Five-facet mindfulness questionnaire, awareness subscale (post-intervention and follow-up)
- NIH toolbox Loneliness (post-intervention and follow-up)
- Healthy Minds Index (post-intervention and follow-up)
- Real-world experiential diversity measured using continuous GPS location tracking (Measured continuously throughout study participation)
- Trajectories of change for self-report outcomes assessed on a weekly basis

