13.0 Procedures Involved

13.1 Study design

This will be a two-group randomized controlled trial assessing the impact of the Healthy Minds Program (HMP), a meditation-based well-being app, on behavioral and self-reported outcomes associated with stress and well-being in 150 individuals. Participants will be adults ages 25 to 65

years who have no significant experience with meditation, have access to a smartphone, and are willing to follow through on all aspects of the protocol. The primary endpoint will be scores on the perceived stress scale. Participants will be randomized to the HMP or waitlist control group at a 2:1 ratio. Prior to randomization, participants will complete initial surveys and a computerized task remotely. Participants assigned to the HMP group will complete a 4-week well-being program remotely using an app on their smartphone. Each week participants will also complete a set of online surveys/tasks. Waitlist control participants will also complete the online surveys/tasks each week for 4 weeks. All participants will complete a final set of follow-up surveys/tasks 3 months later. In addition, we will track participant location using GPS smartphone technology throughout the study.

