20.0 Study Analysis

20.1 Statistical hypotheses

H1: HMP vs. waitlist participants will show (a) lower scores on the perceived stress scale, (b) improved performance on the pattern separation task, and (c) increased "experiential diversity" measured using GPS location tracking.

H2: Within the HMP group, greater decreases in perceived stress will be correlated with improvements/increases in outcomes b-c.

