20.2 Sample size justification

We plan to enroll 150 participants, assigning two-thirds to the HMP group and one-third to the waitlist control group, and anticipate 10% dropout. This sample size affords us 80% power to detect medium effect sizes (d = 0.5) for our primary outcome of perceived stress at p < 0.05. A recent study of the Healthy Minds Program vs. waitlist control (Hirshberg et al., 2021) identified a similar effect size for a composite "distress" measure, which was an aggregate of perceived stress and PROMIS anxiety/depression scores, and another previous study suggested a SD of 0.5 reflects a minimal clinically important differences for the Perceived Stress Scale (Platinga et al., 2017). For correlation analyses, we have 80% power to detect medium-to-large correlations (r = 0.41) at p < 0.0125 (0.05/4 outcomes).

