20.4 Statistical methods

Group differences for the intervention will utilize linear mixed effects models with a random intercept and slope for each participant to account for non-independence of error and to maximize use of data with missing observations. We will conduct Pearson correlation analyses using difference scores between baseline and post-intervention/follow-up timepoints to test whether reductions in perceived stress are associated with behavioral or imaging outcomes hypothesized to contribute to differences in perceived stress.

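### Does the plan leave open whether post-intervention (T5) or follow-up (T6) decides the perceived-stress hypothesis?

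*Combined protocol and SAP*

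**What the plan says.** The statements on perceived stress in the combined protocol and SAP differ in how specific they are.

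- **3.2 Hypotheses:** "Intervention participants will show larger reductions in perceived stress relative to waitlist control participants at post-intervention and follow-up timepoints".
- **3.3, primary tier:** a single entry, "Scores on the perceived stress scale at post-intervention (T5) controlling for baseline (T1").
- **3.3, secondary tier:** each entry carries both visits: "Performance on the behavioral pattern separation task (post-intervention and follow-up/T6") and "PROMIS depression and anxiety (post-intervention and follow-up"). Most of the tertiary and exploratory entries do the same. PSS at T6 is not listed. The exploratory item on weekly self-report trajectories does not name a T6 group comparison.
- **13.1 Study design:** "The primary endpoint will be scores on the perceived stress scale", with no visit.
- **13.2 Schedule:** PSS is collected at T1, T2 to T4, T5 and T6.
- **20.1, H1(a):** "HMP vs. waitlist participants will show (a) lower scores on the perceived stress scale", with no visit.
- **20.2:** "This sample size affords us 80% power to detect medium effect sizes (d = 0.5) for our primary outcome of perceived stress", at p < 0.05, with no visit. The only alpha adjustment (0.05/4) is for the correlations.
- **20.4:** "Group differences for the intervention will utilize linear mixed effects models with a random intercept and slope for each participant". No visit or contrast is named for the group difference.

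**The concern.** The main outcome is hypothesised at two visits, measured at both, and given a formal status at only one. Most other outcomes in 3.3 carry both visits, so the omission for PSS stands out, and Section 20 does not repeat which visit counts.

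Two difficulties could follow. If the benefit fades after T5, one reader might call the first hypothesis met (by 3.3) and another not met (by 3.2) from the same data. If only T6 reaches significance, a report might present it as support for the main hypothesis at an unadjusted 0.05. In addition, a power statement for one visit does not cover a claim that needs two.

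**Working it through.** **Inputs.** From 20.2: 150 enrolled, allocated 2:1 (100 and 50), 10% dropout (135 left: 90 and 45), d = 0.5, p < 0.05, power 80%. Not in the documents, so assumed: a two-sided test, an SD of 1, and the correlation rho between the T5 and T6 test statistics (range 0 to 0.9). Simple two-group comparisons stand in for the mixed model of 20.4.

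**Step 1: reproduce the stated power.** Power = Φ(d / √(1/n₁ + 1/n₂) − 1.96).

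- 90 against 45: 0.5 / √(1/90 + 1/45) = 0.5 / 0.1826 = 2.739, and Φ(2.739 − 1.96) = 78.2% (77.6% by noncentral t).
- 100 against 50: 0.5 / √(1/100 + 1/50) = 0.5 / 0.1732 = 2.887, and Φ(2.887 − 1.96) = 82.3% (81.8% by noncentral t).

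The stated 80% lies between these. It is the power of one comparison at one visit with the whole 0.05. Adjustment for T1, which 3.3 calls for, replaces the SD by √(1 − r²). At 90 against 45 this gives 81.9% for an assumed baseline correlation r = 0.3 and 88.5% for r = 0.5.

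**Step 2: what a two-visit decision rule would do.** With 90 against 45, a true effect of 0.5 SD at both visits for the power column, and no effect at either visit for the false-positive column:

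| rho | Power if both visits must be significant | False-positive rate if either visit may decide |
|---|---|---|
| 0 | 61% | 9.75% |
| 0.5 | 66% | 9.1% |
| 0.7 | 69% | 8.4% |
| 0.9 | 73% | 7.0% |

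At rho = 0 the second column is 0.782² = 0.61 and the third is 1 − 0.95² = 0.0975.

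**Step 3: is either rule in the plan?**

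- *Either visit decides.* No section says so. 3.2 joins the visits with *and*, so a result at T6 alone satisfies neither 3.2 nor 3.3.
- *Both visits required.* 3.2 can be read as a joint prediction, but it is a list of expected findings. The section that assigns primary status is 3.3, and it names T5 alone.
- *T5 decides.* 3.3 says this. 13.1, 20.1 and 20.2 say less about PSS and nothing that conflicts with it.

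**Step 4: follow the two awkward outcomes through.** If T5 is significant and T6 is not, the primary endpoint is met and the follow-up half of the prediction in 3.2 is unsupported. Both statements can be reported together. If T6 is significant and T5 is not, the primary endpoint is not met, and the T6 finding stands outside it.

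**The case for a change.** The strongest case for a change is that durability on the main outcome should have its status fixed in advance, and that the gap looks like an oversight because 3.3 gives both visits for nearly every other measure. The repair would be wording only: list PSS at T6 as secondary, tested after T5, at no cost in alpha or T5 power. It can also be said that requiring both visits loses much more power if the effect wanes. With an unadjusted comparison and a T5-T6 correlation of 0.3 to 0.6, the joint power is 24 to 27% if the T6 effect is halved and about 2.5% if it is zero.

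The observation about the missing tier stands. The weekly-trajectory item does not clearly fill it, since T6 comes about three months after T5. The rest carries less weight. The low joint-power figures follow from the assumed T6 effects: a test with no true effect should rarely be positive, so they do not measure harm done by the wording. Section 3.3 is not a complete inventory either. The Flourishing Measure, the GPAQ and the MIMIS are collected at T1, T5 and T6 and appear in no tier. A T5-then-T6 testing order would correct no stated rule, because the plan sets no testing order for any secondary endpoint. The contrast left unnamed in 20.4 is a separate question about the model; 3.3 already says which visit and which adjustment it must target.

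**Conclusion.** No change is needed. The primary question is decided by PSS at T5 adjusted for T1, and the stated 80% power agrees with that single test (78 to 82%, two-sided, without credit for baseline adjustment). No inflation of the 5% error rate and no loss of the stated power is shown. The 7.0 to 9.75% and 61 to 73% figures describe rules that the plan does not adopt for its primary question, and they rest on assumed correlations.

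What remains is missing detail: PSS at T6 has no tier label, and 13.1 and 20.1 do not repeat the visit. Because 3.2 states the follow-up prediction and 13.2 schedules the measurement, an analyst would report the T6 group difference beside the primary result without letting it replace that result. This conclusion assumes that 3.3, the section that assigns primary status, governs over the broader predictions in 3.2.

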3.3 Primary and secondary study endpoints

Primary endpoints

• Scores on the perceived stress scale at post-intervention (T5) controlling for baseline (T1)

Secondary endpoints

- Performance on the behavioral pattern separation task (post-intervention and follow-up/T6)
- PROMIS depression and anxiety (post-intervention and follow-up)

Tertiary and exploratory endpoints

- Symptoms of PTSD measured using the PCL-5 (post-intervention and follow-up)
- PROMIS sleep disturbances (post-intervention and follow-up)
- Five-facet mindfulness questionnaire, awareness subscale (post-intervention and follow-up)
- NIH toolbox Loneliness (post-intervention and follow-up)
- Healthy Minds Index (post-intervention and follow-up)
- Real-world experiential diversity measured using continuous GPS location tracking (Measured continuously throughout study participation)
- Trajectories of change for self-report outcomes assessed on a weekly basis

4.0 Number of Participants

4.1 Total number of participants

This study will enroll 150 participants at UW-Madison.

4.2 Number of participants expected to be enrolled and screened vs. number of participants needed to complete the study

N/A - Only eligible participants will be enrolled in this study. Participants will be screened prior to enrollment.

4.3 Criteria for "enrolled" participants and replacing withdrawals

Participants will be considered enrolled after signing the consent form. If participants leave the study prior to randomization, they will be replaced. However, participants who leave the study after being randomized will not be replaced.

5.0 Inclusion and Exclusion Criteria

5.1 Screening

After reading a description of the study, individuals who are interested in participating will complete an Online Eligibility Survey in REDCap. The survey will automatically inform individuals who do not meet eligibility criteria for auto-exclusion items that they are not eligible. Other items will be reviewed by study staff to determine eligibility. We will review those responses and inform potential participants about their eligibility via email. We will retain all screening data to maintain a record of reasons individuals are not eligible for the study.

5.2 Inclusion criteria

- 25 to 65 years old
- Individual can read, write, speak, and understand English
- Able to provide informed consent
- Willing and able to complete all study procedures, including the Healthy Minds Program
- Has access to an Android or iPhone (Apple/iOS) smartphone that can download apps from Google Play or the Apple App Store
- For payment purposes, must be a US citizen or a permanent US resident (green card holder)

5.3 Exclusion criteria

- Extensive experience in meditation practice (e.g., regular daily meditation practice for the past 6 months or regular weekly meditation practice for the past 12 months), experience in substantively similar meditation training programs (e.g., attended a meditation retreat or a yoga/body practice retreat with a significant mediation component), or substantial previous use of the Healthy Minds Program app
- Individuals will be excluded if they previously participated in substantively similar research at our Center at the discretion of the investigator due to similar tasks being used in certain studies

- History of psychosis
- History of mania
- Current psychopathology that interferes with study participation

5.4 Specific population

This study will include a sample of adults between 25 and 65 years old that is demographically representative of the overall population of the United States. We will exclude individuals under age 25 and over age 65 due to age-related differences in the brain regions we are studying. Young people (under age 25) have brains that are still developing, while older people (over age 65) are expected to start showing age-related hippocampal decline and behavioral changes that would confound our ability to test hypotheses related to stress and the hippocampus.

6.0 Special Populations

6.1 The study will not enroll individuals from any of the following populations. However, pregnant women may be incidentally enrolled. We will not be screening for pregnancy because there are no known additional risks to pregnant persons or fetuses from study procedures/intervention. This study involves activities that are of no greater risk than typical activities of daily living. Assessments will be conducted entirely on a smartphone or other digital device and consist of completing questionnaires about health and well-being, completing a memory task, and passive location tracking. The intervention is smartphone-based and consists of listening to podcast-style lessons about well-being and completing meditation practices. We have chosen research activities that minimize time and burden for participants that are similar to typical activities encountered in daily life; therefore, any risk involved is minimal. There is no reasonable expected risk of the study procedures/intervention on pregnant women or fetuses, so preclinical studies are not scientifically appropriate. Additionally, this research is unrelated to decisions regarding termination of pregnancy and viability of a neonate.

\Box C	Children/Minors
□ P	regnant persons / fetuses
□ P	risoners
□ P	articipants with impaired decision-making capacity
6.2 The stud	ly will not enroll individuals from any of the following populations.
\square N	Non-English speaking participants
□ I1	lliterate or Low Literacy participants
□ P	articipants with visual or hearing impairments
	tatus Relationship: Individuals with a status relationship with the PI or other study eam members (e.g., employees, students, family members)

6.3 The study will not specifically target enrollment of individuals from any of the following populations. However, we will not ask questions about every category (e.g., veterans/military personnel), and may, therefore, unknowingly enroll individuals who belong to some of the following populations.

PROTOCOL TITLE: Brain and Meditation (BAM) Study

Individuals who are receiving inpatient or outpatient services for mental illness,
developmental disability, or alcohol and other drug abuse (AODA)
Individuals who are protectively placed by a court in a treatment facility
Veterans/Military Personnel
Emancipated minors
Anyone especially vulnerable to manipulation or inducements for participation as a
result of their illness or socioeconomic condition

7.0 Recruitment Methods

7.1 Sources of participants

We will recruit from an ongoing companion study (PI: [name]; Title: "Individual differences in affective chronometry"; IRB Protocol: 2018- 0937), the community, research recruitment services, and the Participant Registry at the Center for Healthy Minds (IRB Protocol: 2019-0330).

7.2 Identifying participants

Research candidates will self-identify in response to advertisements, such as flyers, website ads (e.g., on the Center for Healthy Minds website, Craigslist, and/or other relevant websites), email ads, and ads on research recruitment services (e.g., Prolific). Another method of recruitment will be contacting participants from the ongoing companion study who have expressed interest in other research studies. It will be made clear that this intervention study is separate from the companion study and that participation is fully voluntary. We will recruit these individuals based on whether they self-identified as having interest in other studies. Finally, we may recruit individuals from the Participant Registry at the Center for Healthy Minds who previously indicated interest in being contacted about research studies.

